2 PROTOCOL SYNOPSIS

Title A Phase 3, Rollover Study to Evaluate the Safety and Efficacy of Long-term Treatment With Lumacaftor in Combination With Ivacaftor in Subjects Aged 6 Years and Older With Cystic Fibrosis, Homozygous for the *F508del-CFTR* Mutation

Clinical Phase and Clinical Study Type Phase 3, safety and efficacy

Objectives Primary Objective

To evaluate the long-term safety and tolerability of lumacaftor in combination with ivacaftor in subjects aged 6 years and older with cystic fibrosis (CF), homozygous for the *F508del-CFTR* mutation, who are in the Treatment Cohort

Secondary Objectives

- To evaluate the long-term efficacy and durability of lumacaftor in combination with ivacaftor for subjects in the Treatment Cohort
- To evaluate the post-treatment safety of lumacaftor in combination with ivacaftor for subjects in the Observational Cohort

Endpoints **Primary Endpoint**

Treatment Cohort

Safety and tolerability assessments of long-term treatment of lumacaftor in combination with ivacaftor based on adverse events (AEs), clinical laboratory values (serum chemistry, hematology, coagulation studies, and urinalysis), standard 12-lead electrocardiograms (ECGs), vital signs, pulse oximetry, ophthalmological examinations, and spirometry

Observational Cohort

Not applicable

Secondary Endpoints

Treatment Cohort

The following efficacy endpoints will be analyzed using baseline values in the previous study (i.e., Study VX14-809-109 [Study 109], Study VX13-809-011B [Study 011B], or Study VX13-809-011B Lung Clearance Index [LCI] Substudy [Study 011B LCI Substudy]):

- Absolute change from baseline in LCI_{2.5} (subjects from Study 109 and the Study 011B LCI Substudy only)
- Absolute change from baseline in sweat chloride
- Absolute change from baseline in body mass index (BMI)
- Absolute change from baseline in Cystic Fibrosis Questionnaire-Revised (CFQ-R) respiratory domain score

The following efficacy endpoints will be analyzed using baseline values in the current study (Study VX15-809-110 [Study 110]):

- Absolute change from baseline in LCI_{2.5} (subjects from Study 109 and the Study 011B LCI Substudy only)
- Absolute change from baseline in sweat chloride
- Absolute change from baseline in BMI

- Absolute change from baseline in CFQ-R respiratory domain score

Observational Cohort

Safety, as determined by serious adverse events (SAEs)

Other Secondary Endpoints

Treatment Cohort

The following efficacy endpoints will be analyzed using baseline values in the previous study (i.e., Study 109, Study 011B, or Study 011B LCI Substudy):

- Absolute change from baseline in LCI_{5.0} (subjects from Study 109 and the Study 011B LCI Substudy only)
- Absolute change from baseline in percent predicted forced expiratory volume in 1 second (ppFEV₁)
- Relative change from baseline in ppFEV₁
- Absolute change from baseline in BMI-for-age z-score
- Absolute change from baseline in weight
- Absolute change from baseline in weight-for-age z-score
- Absolute change from baseline in height
- Absolute change from baseline in height-for-age z-score
- Absolute change from baseline in Treatment Satisfaction Questionnaire for Medication (TSQM) domains
- Time-to-first pulmonary exacerbation, including pulmonary exacerbations in the previous study and the current study (subjects from Study 109 only)
- Event of having at least 1 pulmonary exacerbation, including pulmonary exacerbations in the previous study and the current study (subjects from Study 109 only)
- Number of pulmonary exacerbations, including pulmonary exacerbations in the previous study and the current study (subjects from Study 109 only)

The following efficacy endpoints will be analyzed using baseline values in the current study (Study 110):

- Absolute change from baseline in LCI_{5.0} (subjects from Study 109 and the Study 011B LCI Substudy only)
- Absolute change from baseline in ppFEV₁
- Relative change from baseline in ppFEV₁
- Absolute change from baseline in BMI-for-age z-score
- Absolute change from baseline in weight
- Absolute change from baseline in weight-for-age z-score
- Absolute change from baseline in height
- Absolute change from baseline in height-for-age z-score
- Absolute change from baseline in TSQM domains
- Time-to-first pulmonary exacerbation in the current study (subjects from Study 109 only)
- Event of having at least 1 pulmonary exacerbation in the current study (subjects from Study 109 only)
- Number of pulmonary exacerbations in the current study (subjects from Study 109 only)

The following efficacy endpoints will also be analyzed:

- Rate of change in LCI_{2.5} (subjects from Study 109 and the Study 011B LCI

Substudy only)

- Rate of change in LCI₅₀ (subjects from Study 109 and the Study 011B LCI Substudy only)
- Rate of change in ppFEV₁

Observational Cohort

Not applicable

Number of Subjects Approximately 256 subjects are potentially eligible to be enrolled into Study 110: approximately 200 subjects from Study 109 and approximately 56 subjects from Study 011B, if eligible.

Study Population Male and female subjects aged 6 years and older with CF who are homozygous for the *F508del-CFTR* mutation and who participated in Study 109 or Study 011B

Investigational Drug **Active substance:** lumacaftor and ivacaftor (fixed-dose combination with lumacaftor and ivacaftor)
Activity: CFTR corrector and potentiator (chloride ion [Cl⁻] secretion)
Strength and Route of Administration: lumacaftor (LUM) 100-mg/ivacaftor (IVA) 125-mg tablets for oral administration in subjects aged 6 through 11 years and LUM 200-mg/IVA 125-mg tablets for oral administration in subjects aged 12 years and older
Dose investigated: LUM 200 mg every 12 hours (q12h)/IVA 250 mg q12h (2 × LUM 100-mg/IVA 125-mg tablet q12h) for subjects aged 6 through 11 years and LUM 400 mg q12h/IVA 250 mg q12h (2 × LUM 200-mg/IVA 125-mg tablet q12h) for subjects aged 12 years and older

Study Duration Treatment Cohort
 For the Treatment Cohort, study drug will be administered for approximately

96 weeks (or until commercial availability for eligible subject [REDACTED]) with a Safety Follow-up Visit 4 weeks [\pm 7 days] after the last dose).

Observational Cohort

For the Observational Cohort, maximum subject participation will be approximately 2 years.

Study Design This is a Phase 3, multicenter study in subjects aged 6 years and older with CF who are homozygous for the *F508del-CFTR* mutation and who participated in Study 109 or Study 011B. Study 110 is designed to evaluate the safety and efficacy of long-term treatment of lumacaftor in combination with ivacaftor.

This study consists of a Treatment Cohort and an Observational Cohort. The Treatment Cohort and the Observational Cohort will be enrolled in parallel.

Treatment Cohort

The following subjects from Study 109 or Study 011B who meet the study criteria and elect to enroll in Study 110 are eligible for enrollment in the Treatment Cohort:

- Subjects who completed 24 weeks of study drug treatment (i.e., lumacaftor in combination with ivacaftor or placebo) in Study 109 or completed 24 weeks of study drug treatment and the Week 26 Safety Follow-up in Study 011B (NOTE: the last dose of study drug is the evening dose administered the day before the Week 24 Visit or the dose at the Week 24 Visit [based on the applicable protocol version for which a subject screens (provides consent/assent) under] in Study 109 or the evening dose administered the day before the Week 24 Visit in Study 011B)
- Subjects who are not receiving study drug treatment at the end of the Treatment Period in Study 109 or Study 011B (NOTE: subjects from Study 011B have a planned Washout Period from Week 24 to Week 26 and must still complete the Week 26 Safety Follow-up), including subjects who require study drug interruption to be either continued or initiated at Day 1 in Study 110, AND who have received Vertex approval for entry

Subjects who prematurely discontinued study drug treatment are not eligible for enrollment in the Treatment Cohort.

The Treatment Cohort will be open-label and will consist of the following dose regimens:

- LUM 200 mg q12h/IVA 250 mg q12h (subjects aged 6 through 11 years)
- LUM 400 mg q12h/IVA 250 mg q12h (subjects aged 12 years and older)

Subjects who turn 12 years of age in the previous study or Day 1 of this rollover study will begin receiving LUM 400 mg q12h/IVA 250 mg q12h on Day 1. Subjects who turn 12 years of age after the Day 1 Visit of this rollover study will begin receiving LUM 400 mg q12h/IVA 250 mg q12h at their next scheduled visit.

Observational Cohort

The following subjects from Study 109 or Study 011B who meet the study criteria and elect to enroll in Study 110 are eligible for enrollment in the Observational Cohort:

- Subjects who received at least 4 weeks of study drug in Study 109 or Study 011B and completed visits up to Week 24 of Study 109 or Week 26 of Study 011B but who are not eligible for the Treatment Cohort with lumacaftor in combination with ivacaftor
- Subjects who received at least 4 weeks of study drug in Study 109 or Study 011B (and did not prematurely discontinue study drug treatment) and completed visits up to Week 24 of Study 109 or Week 26 of Study 011B but who elect not to continue treatment with lumacaftor in combination with ivacaftor

Subjects in the Observational Cohort will not receive study drug and will have regularly scheduled telephone calls for approximately 2 years after their last dose of study drug in Study 109 or Study 011B to assess the post-treatment safety of lumacaftor and ivacaftor combination therapy.

Assessments Efficacy Assessments

Subjects from Study 109 and the Study 011B LCI Substudy only: LCI (i.e., LCI_{25} represents the number of lung turnovers required to reduce the end tidal inert gas concentration to 1/40th of its starting value and LCI_{50} represents the number of lung turnovers required to reduce the end tidal inert gas concentration to 1/20th of its starting value)

Subjects from Study 109 only: Documentation of other events related to outcomes (e.g., pulmonary exacerbations), [REDACTED]

All subjects: Spirometry, sweat chloride, weight, height, BMI, CFQ-R, and TSQM

Safety Assessments

AEs, clinical laboratory assessments (serum chemistry, hematology, coagulation studies, and urinalysis), standard 12-lead ECGs, vital signs, pulse oximetry, ophthalmologic examinations, spirometry, and physical examinations (PEs)

Statistical Analyses Statistical analysis details will be provided in the Statistical Analysis Plan (SAP). A stable draft SAP will be available before the first subject first dose in the

current open-label rollover study, which will be finalized before the clinical data lock for the study.

For the Treatment Cohort, analyses will be repeated for current dosing period, cumulative dosing period (efficacy only), and active dosing period. All analyses will be provided using all data, regardless of whether the subjects turn 12 years of age and subsequently switch to LUM 400 mg q12h/IVA 250 mg q12h [REDACTED]

[REDACTED]

For safety analysis, only descriptive analyses will be performed (i.e., no formal statistical testing will be performed). Summaries of treatment-emergent AEs (TEAEs) using number and percentages of subjects as well as number of events per 100 patient-years (number of events adjusted for the total duration of exposure) will be provided. Summaries of clinical laboratory results, ECGs, vital signs, and pulse oximetry, including their raw values and change from baseline values at each visit, will be provided. For the analysis of slit lamp lens, the number and percentage of subjects with shift changes from baseline (normal versus abnormal) will be tabulated. Ophthalmological examination findings will be presented as a listing. Spirometry data will also be summarized descriptively at each visit by category.

For continuous efficacy variables, raw values and absolute change (or relative change) from baseline at each visit will be summarized and plotted. Descriptive statistics including number of subjects (n), mean, standard deviation (SD), standard error (SE), median, minimum, and maximum will be provided. In addition, 95% CI of the mean will be presented. For the analyses of LCI and ppFEV₁, a mixed-effect repeated-measure model (MMRM) will be fitted for the cumulative dosing period, including visits from the previous Study 109 and Study 011B and visits from the current Study 110 based on Integrated Full Analysis Set (IFAS). In the MMRM models for the cumulative dosing period, the absolute change from baseline of the previous study (including all predose measurements at each visit in the cumulative dosing period, both on-treatment measurements and measurements after treatment discontinuation), will be included as the dependent variable; treatment group, visit, and treatment-by-visit interaction as fixed effects; and subject as a random effect with adjustment for previous study (Study 109 versus Study 011B), weight (<25 kg versus ≥25 kg), and ppFEV₁ severity (<90 versus ≥90), both as determined at screening in the previous study. In the analysis of LCI, baseline LCI value will also be included as a continuous covariate in the MMRM model. The result obtained from the model will be the treatment effect at each postbaseline visit. The estimated mean treatment effect, a 95% CI, and a 2-sided *P* value will be provided. The rate of change in LCI and ppFEV₁ during the active dosing period will be analyzed using linear mixed-effects models (LMM).

For the Observational Cohort, summaries will only be provided for the disposition, demographic and baseline characteristics, and SAEs, based on all enrolled subjects in that cohort.

IDMC Safety Reviews An independent data monitoring committee (IDMC) will be formed using the [REDACTED]. The IDMC objectives and operational details will be defined in a separate document (IDMC Charter), which will be finalized before the first IDMC review meeting. The IDMC will conduct regular planned reviews of study data for the purpose of safety monitoring as outlined in the IDMC Charter.

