^o An ophthalmologic examination will be conducted by a licensed ophthalmologist or optometrist (Section 11.7.6). Subjects with documentation of bilateral lens removal do not need the ophthalmologic examination. If a cataract or lens opacity is identified and determined to be clinically significant by a licensed ophthalmologist or optometrist at the Day 1 examination (also see Footnote b), the subject will be notified. After discussion with the site principal investigator and in collaboration with the Vertex medical monitor, the subject may elect to participate or not to participate in the study. If the subject continues in the study, more frequent ophthalmologic monitoring should be considered. If a cataract or lens opacity is identified and determined to be clinically significant by a licensed ophthalmologist or optometrist after dosing, the subject will be notified. After discussion with the site principal investigator, and in collaboration with the Vertex medical monitor, the subject may elect to continue or discontinue the study. If the subject discontinues study drug, they should complete the Early Treatment Termination Visit and Safety Follow-up Visit (see Section 8.1.1.3 for Early Treatment Termination). If the subject continues, more frequent ophthalmologic monitoring should be considered.

^p Subjects may complete the ophthalmologic examination within ± 1 week of the scheduled visit.

^q An ophthalmologic examination will be conducted by a licensed ophthalmologist or optometrist at the Week 96 Visit (or the Early Treatment Termination Visit if the subject does not have a Week 96 Visit) OR the Safety Follow-up Visit (Section 11.7.6). Subjects with documentation of bilateral lens removal do not need the ophthalmologic examination.

^r Symptom-directed physical examinations will occur at any time during the study if triggered by AEs or if deemed necessary by the investigator (Section 11.7.4).

^s All standard 12-lead ECGs will be performed before study drug dosing and after the subject has been seated or supine for at least 5 minutes (Section 11.7.5). The ECG will be performed before any other procedures that may affect heart rate (e.g., blood draws).

^t ECGs collected on Day 1 before study drug dosing will be performed in triplicate.

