8.2.3 Rationale for Study Assessments

The safety assessments are standard parameters for clinical studies in drug development and are generally recognized as reliable, accurate, and relevant to the study of subjects with CF. Ophthalmologic examinations were added to the standard safety assessments.

Ophthalmologic Examinations: A juvenile rat toxicity study performed to support dosing of ivacaftor in subjects <2 years of age demonstrated lens opacities in some animals.²¹ Prior studies in rats and dogs of older age did not demonstrate similar findings. Given substantial differences between human and rat lens development, the finding is of unlikely relevance to humans. Periodic ophthalmologic examinations for children aged 11 years and younger receiving ivacaftor are being performed to confirm this interpretation. The overall data acquired to date does not suggest an association between ivacaftor treatment and cataract development; however, a potential association has not been fully excluded.

LCI Assessment (Subjects From Study 109 and the Study 011B LCI Substudy Only): LCI is a measure of ventilation inhomogeneity that is based on tidal breathing techniques which have been evaluated in patients as young as infants.^{31,32} Studies have shown that LCI correlates with FEV₁ in its ability to measure airway disease in patients with impacted spirometry assessment but can also detect lung disease at an earlier stage than spirometry.^{28,33} Furthermore, data from Study VX10-770-106 in CF patients with an FEV₁ >90% showed LCI to be a more sensitive outcome measure than FEV₁.

Spirometry: Because lung disease is the major cause of morbidity and mortality for patients with CF, CF lung disease is the desired primary target of lumacaftor therapy. FEV₁, as measured by spirometry, is the most widely implemented standardized assessment to evaluate lung function in CF and is therefore included as an assessment.

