11.7.6 Ophthalmologic Examination

Subjects will undergo an ophthalmologic examination at the Day 1 and Week 48 Visit and at the Week 96 Visit (or the Early Treatment Termination Visit if the subject does not have a Week 96 Visit) OR the Safety Follow-up Visit (NOTE: subjects may complete the ophthalmologic examination within ± 1 week of the scheduled Week 48, Week 96/Early Treatment Termination, and Safety Follow-up Visits), which includes

- measurement of best corrected distance visual acuity of each eye
- measurement of lens refracting power (e.g., autorefractor or ophthalmoscopy streak following cycloplegia)
- pharmacologically dilated examination of the lens with a slit lamp

These examinations must be conducted by a licensed ophthalmologist or optometrist. Subjects with documentation of bilateral lens removal do not need the ophthalmologic examination.

If a cataract or lens opacity is identified and determined to be clinically significant by a licensed ophthalmologist or optometrist at the Day 1 examination, the subject will be notified. After discussion with the site principal investigator, and in collaboration with the Vertex medical monitor, the subject may elect to participate or not to participate in the study. If the subject continues in the study, more frequent ophthalmologic monitoring should be considered.

If a cataract or lens opacity is identified and determined to be clinically significant by a licensed ophthalmologist or optometrist after dosing, the subject will be notified. After discussion with the site principal investigator and in collaboration with the Vertex medical monitor, the subject may elect to continue or discontinue the study. If the subject discontinues study drug, they should complete the Early Treatment Termination Visit and Safety Follow-up Visit (see Section 8.1.1.3 for Early Treatment Termination). If the subject continues, more frequent ophthalmologic monitoring should be considered.

Additional ophthalmologic examinations may be conducted at the discretion of the investigator. The Vertex medical monitor or designee should be notified of any additional ophthalmologic examinations.

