10.4.6 Ophthalmological Examinations

Treatment Cohort Period 1

For the analysis of slit lamp lens, the number and percentage of subjects with shift changes from previous study baseline (normal versus abnormal) will be tabulated for the Previous Study Period based on the Safety Set, Current Study Period based on 110 Safety Set, and Cumulative Study Period based on the Safety Set at each scheduled time point following the safety presentation format in Section 10.1.2. Ophthalmological examination findings will also be presented as a data listing.

Treatment Cohort Period 2

Ophthalmological examination findings in Treatment Cohort Period 2 will be presented as a data listing.

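### The only lens table has two levels, so worsening from an abnormal baseline cannot appear in it and incidental and clinically significant opacities count alike

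*Protocol*

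**What the plan says.** The protocol synopsis (Section 2, Statistical Analyses) states: "For the analysis of slit lamp lens, the number and percentage of subjects with shift changes from baseline (normal versus abnormal) will be tabulated". The next sentence adds: "Ophthalmological examination findings will be presented as a listing". Protocol 12.4.4.6 repeats both elements, for the current and active dosing periods at each scheduled time point.

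For Treatment Cohort Period 1, SAP 10.4.6 keeps the two levels and fixes the reference point: "the number and percentage of subjects with shift changes from previous study baseline (normal versus abnormal) will be tabulated". This applies to the Previous, Current and Cumulative Study Periods, again with a listing. For the French extension the SAP plans no lens table: "Ophthalmological examination findings in Treatment Cohort Period 2 will be presented as a data listing". Neither document contains any other lens-specific tabulation.

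Protocol 8.2.3 gives the reason for examining the lens. Opacities were seen in juvenile rats, and although human data so far do not suggest a link with ivacaftor, "a potential association has not been fully excluded". Ophthalmological examination is a named component of the primary endpoint (Protocol 7.1, SAP 6.1).

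Protocol 11.7.6 describes the examination. Visual acuity is specified by eye: "measurement of best corrected distance visual acuity of each eye". The lens item names no eye: "pharmacologically dilated examination of the lens with a slit lamp". The same section and the ophthalmology footnote to Table 3-1 call for a clinical-significance judgement by the examiner, with notification and discussion to follow "If a cataract or lens opacity is identified and determined to be clinically significant by a licensed ophthalmologist or optometrist after dosing".

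**The concern.** The examination was added to answer one question, whether lens opacities appear or progress under treatment. A two-level shift answers part of it. It counts lenses that go from normal to abnormal, but it has no cell for a lens that was abnormal and became worse. It also does not separate findings the examiner considers unimportant from those that matter. The count can therefore be too low for progression and too high for clinically relevant opacity. At stake is how well a named component of the primary safety endpoint can be read from its own table. By contrast, SAP Appendix H splits transaminases into several bands.

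**Working it through.** The documents state no figure for a lens outcome. The only precision figures, in Protocol Table 12-1, concern CF lung incidence at n = 256. They reproduce as Wald intervals (for example 0.1 ± 1.96 × √(0.1 × 0.9/256) = 0.063 to 0.137) but do not bear on this point. The check is therefore one of logic.

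**Step 1: what the table can show.** Grade each eye 0 (normal), 1 (abnormal, not clinically significant) or 2 (abnormal, clinically significant). Take every baseline-to-follow-up pattern for two eyes in which at least one eye worsens and neither improves. The numbers of such patterns, by baseline, are:

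- (0,0): 8
- (0,1) and (1,0): 5 each, 10 in total
- (1,1): 3
- (0,2) and (2,0): 2 each, 4 in total
- (1,2) and (2,1): 1 each, 2 in total

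The total is 8 + 10 + 3 + 4 + 2 = 27.

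**Step 2: how many patterns each table shows as a worsening.**

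| Table | Shown | Not shown |
|---|---|---|
| Two levels, one result per subject (abnormal if either eye is) | 8 | 19 |
| Two levels, by eye | 20 | 7 |
| Three levels, worse eye per subject | 19 | 8 |
| Three levels, by eye | 27 | 0 |

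The first row shows only the 8 patterns that start from (0,0). The third row adds those in which the worse eye moves from 1 to 2: 4 from (0,1), 4 from (1,0) and 3 from (1,1), so 8 + 11 = 19. These are counts of patterns, not expected frequencies. They show which kinds of change a table can register, not how often children will have them.

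**Step 3: clinical significance.** Both two-level versions put grades 1 and 2 in one cell, whichever way the eyes are handled. A move from 0 to 1 and a move from 0 to 2 count the same.

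**Step 4: baseline.** Protocol 12.4.1 takes the last value before each dosing period. SAP 10.4.6 takes the previous-study baseline in all periods. Under the SAP, an opacity that arose during Study 109 or 011B does register as a shift from normal. Further worsening of that lens in Study 110 changes nothing in the table.

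**Step 5: size.** Let p be the share of children abnormal at baseline and r their risk of a new or worse opacity relative to the others. With one result per subject, the share of such events missing from the table is r·p/(1 − p + r·p). Neither input is in the documents. Assuming p = 1% and r = 1 gives 1.0%. Assuming p = 15% and r = 3 gives 0.45/(0.85 + 0.45) = 34.6%. The result is set entirely by the assumptions, so no magnitude is claimed.

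**The case against.** The strongest reply is that the lens table does not stand alone. Every ophthalmological finding is listed. The adverse event definition covers worsening of an existing condition (Protocol 13.1.1.1), and study assessments judged a clinically significant worsening are documented as adverse events (13.1.1.2). Treatment-emergent events include those that increase in severity, and they are tabulated by system organ class and preferred term (Protocol 12.4.4.1, SAP 10.4.1). A reported cataract, or the progression of one, is therefore counted whatever the baseline lens status.

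This stands, and it rules out reading the table's gap as events hidden from the study. It does not close the gap. A listing has no counts or denominators. The adverse event route depends on investigator judgement. The assessments that 13.1.1.2 gives as examples do not include ophthalmology, although that list is not exhaustive. The SAP defines no lens category among its adverse events of special interest.

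A reader might also infer three stronger things:

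- *A new opacity in the second eye cannot register.* That follows only if the two eyes are collapsed into one result per child. Counting subjects points that way, but no rule is stated and a by-eye table would fit the same words. What is missing is a rule.
- *Children who enter Study 110 with a clinically significant opacity are the ones the table cannot follow.* SAP 10.4.6 uses the previous-study baseline, so an opacity acquired in the parent study is counted as a shift. Only its later course is not.
- *A definite share of events is missed.* Step 5 shows that any such percentage comes from assumed inputs. The 256 children are also only those potentially eligible, not the safety-set denominators.

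Finally, the documents do not include the eCRF. They show that clinical significance is judged for a cataract or lens opacity, but not that it is recorded as a data field, for each eye, or for every abnormal lens. No opacity grading scale is defined. This limits the remedy.

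**Conclusion.** The point holds for the table itself. As planned, the only lens-specific tabulation cannot show worsening from an abnormal baseline and does not separate incidental from clinically significant opacity, although the examiner is asked to make that judgement. It also leaves the handling of two eyes undefined. On its own it cannot describe lens progression. Together with the listing and the adverse event tables, the study retains much of the information, but without counts and denominators for progression that is not reported as an adverse event.

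No size can be given, because baseline prevalence is not in the documents. If few children were abnormal at the parent-study baseline, the loss for progression is small. The mixing of trivial and significant findings remains either way. The conclusion rests on the wording of Protocol 12.4.4.6 and SAP 10.4.6 and affects no sample size, error rate or test, since safety is descriptive throughout.

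**What to change.** In Protocol 12.4.4.6 and SAP 10.4.6, with the synopsis sentence conformed:

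1. Replace the two-level shift with three levels: normal, abnormal not clinically significant, abnormal clinically significant. State that the category uses the ophthalmologist's or optometrist's determination under Protocol 11.7.6.
2. Add one row counting subjects who, since the previous-study baseline, have a new clinically significant lens opacity or a move from not clinically significant to clinically significant.
3. Tabulate by eye where the eCRF records the lens by eye. Otherwise classify each subject by the worse eye and say so.
4. Keep the listing.

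The cost is a change of wording and one reprogrammed table, provided the clinical-significance judgement is in the database, which should be confirmed first. Cells will be sparser. Two limits remain. Worsening within a category will not show, because no grading scale is defined. Under the worse-eye rule, 8 of the 27 patterns above also stay unseen, so the listing is still needed.
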